Safety and Tolerability Of Allogeneic Mesenchymal Stromal Cells in Pediatric and Adult Inflammatory Bowel Disease (STOMP)

SPONSOR

[name], MBChB

PRINCIPAL INVESTIGATOR

[name]

CO-INVESTIGATORS

[name], MS

[name]

[name]

[name]

STATISTICIANS:

[name]

CENTER

Children's National Medical Center

Center for Cancer and Blood Disorders

[name]

[name]

[contact]

Emergency Contact Information

Role in Study	Name	Email and Telephone Number
Sponsor	[name]., FRACP, FRCPA	[contact]/ [contact]
Principal Investigator	[name]	[contact]/ [contact]
Co-investigators	[name] [name], MS [name] [name]	[contact]/[contact] [contact]/[contact] [contact]/[contact] [contact]/[contact]
Institutional Review Board	CNMC Institutional Review Board	[name]/[contact]
Study Coordinator	[name]	[contact]

Name of Sponsor/Company: [name]., FRACP, FRCPA
Title of Study: Safety and Tolerability of Allogeneic Mesenchymal Stromal Cells in Pediatric and Adult Inflammatory Bowel Disease (STOMP trial)
Study Center(s): Children's National Medical Center (CNMC)
Principal Investigator: [name] Co-investigators: [name], [name], MS, [name], [name]
Objectives: Primary Objective: This is a pilot phase 1 study of Mesenchymal Stromal Cells (MSCs) for treatment of children and young adult patients with refractory Crohn's Disease (CD) or ulcerative colitis (UC). The primary aim is to evaluate safety and tolerability of the intervention. Secondary Objectives: 1. Examine the effects of 4 weekly infusions of MSCs on clinical indices, and endoscopic scores when available. 2. Examine inflammatory and immunologic effects of MSC infusions on peripheral and intestinal mucosal biomarkers including, but not limited to, serum C-reactive protein, fecal calprotectin, anti-HLA antibodies, and viral specific T-cell activity before and after treatment.
Study Design: This study is a pilot phase 1 study of patients with moderately to severely active Crohn Disease (CD) and ulcerative colitis (UC) (≥ 18 years, Mayo score: ≥ 6 or CDAI: > 220 ; < 18 years, Pediatric Crohn's Disease Activity Index (PCDAI) > 30) or Pediatric Ulcerative Colitis Activity Index (PUCAI) > 34). [1] [2] A fixed dose will be studied: 1×10^6 cells/kg administered intravenously (IV) weekly for 4 consecutive weeks, with the option of an additional 4 weeks of treatment, at the discretion of the principal investigator. The primary outcomes are regimen-related toxicity, defined in section 5. Toxicity will be scored as a binary variable indicating occurrence or non-occurrence over a monitoring interval from the start of MSC therapy to 45 days after the last infusion. Based on the planned administration schedule of 4 weeks, the total toxicity monitoring period will have duration $28 + 45 = 73$ days. If additional weekly doses are administered, the safety assessment phase will be 45 days after the last dose given.

Three young adult patients (ages 17≤22 years) will be enrolled, staggered by at least 7 days, and monitored for toxicity over a period of 73 days. Infusions are administered over the first 28 days, followed by a 45 day monitoring period. If we observe no severe (grade 3 or worse) adverse events in the young adult cohort, we will wait a minimum of 45 days after the last MSC administration before beginning to enroll 3 more patients, ages 12≤16 (pediatric cohort). If we observe a severe (grade 3 or worse) adverse event occurring at any time from the start of therapy to 45 days following the last MSC administration in the young adult cohort we will stop the study. If we observe no severe adverse events attributable to MSCs in the young adult cohort but a severe (grade 3 or worse) adverse event occurring at any time from the start of therapy to 45 days following the last MSC administration in the pediatric cohort we will stop the study. A maximum of 6 patients will be enrolled. Assuming an accrual rate of 3-4 patients per year, it is anticipated that it will require at least 18-24 months to accrue all 6 patients.

Eligibility

This protocol allows for the treatment of both male and female pediatric and young adult patients, between the ages of 12 ≤ 22 years, with active moderate to severe CD or UC, who have failed to respond to, or are intolerant of, biologic therapy.

Inclusion criteria

- For the young adult cohort, patients must be ages 17 ≤ 22 years
- For the pediatric cohort, patients must be ages 12 ≤ 16 years
- Patients must have moderate-severely active CD or UC (defined in section 2.3), and documented active disease on flexible sigmoidoscopy, colonoscopy or MR enterography within the preceding 2 months.
- Patients who have failed or are intolerant of biologic therapy. Specifically, the patient will have recurrence or persistence of active disease despite current or past treatment with a biologic. At the time of enrollment, study subjects may be currently receiving 5-aminosalicylates, corticosteroids (\leq 20 mg daily or up to 0.5 mg/kg/day if weight <40 kg), methotrexate, 6MP/azathioprine, or a biologic (either as monotherapy or in combination). During the treatment phase, if the treating physician thinks that a medication dose should be lowered to avoid side effects, this should be recorded.
- Patient or parent/guardian capable of providing informed consent.

Exclusion criteria

- Patients <12 years of age or >22 years of age
- Pregnant or breastfeeding. Serum pregnancy test must be negative at screening for female subjects of childbearing potential. Urine pregnancy test must remain negative at each of 4 infusion visits.
- Patients with toxic mega-colon or intestinal perforation
- Evidence of autoimmune chronic active hepatitis or sclerosing cholangitis.
- Patients with fever $>39^{\circ}\text{C}$ or clinically significant active infection within 1 week (i.e. chronic infections including Hepatitis B/C or HIV or acute infections, including urinary tract infection and respiratory tract infection)
- Received an agent not approved by the FDA for marketed use in any indication or any small molecule inhibitors (i.e. naltrexone) within 60 days of enrollment.
- Subjects who are taking greater than 20 mg (or if body weight <40 kg, 0.5 mg/kg) of prednisone daily.

- Clinically significant abnormal biochemical and hematological parameters, including:
 - Neutrophil count < 1000 cells/mm³
 - Hemoglobin < 8 g/dL
 - Platelet count ≤ 130 cells/mm³
 - Creatinine ≥ 1.2 x the upper limit of normal
 - Alanine aminotransferase (ALT) and/or aspartate aminotransferase (AST) ≥ 2x the upper limit of normal
 - Conjugated bilirubin greater than 1.2 mg/dL
- Has active infection with enteric pathogens as evidenced by positive microbiological culture of stool or C.difficile toxin PCR.
- Had bowel surgery other than perianal procedures (fistulotomy, seton placement, abscess drainage) within 3 months of enrollment.
- Has uveitis
- Has known pulmonary disease, excluding mild intermittent asthma

Primary Endpoints

- Safety and tolerability of the intravenous administration of human allogeneic bone marrow-derived MSCs to children and young adults with IBD, measured by the frequency of any SAEs, AEs and/or early treatment discontinuations.

Secondary Endpoints

- Magnitude of decrease in clinical index (for young adults we will use the CDAI and Mayo, and for children the PCDAI and PUCAI) relative to baseline, reporting the average decline and 95% confidence limit.
- Changes in biomarkers of inflammation and immunogenicity (i.e. C-reactive protein, fecal calprotectin, anti-HLA antibodies, viral-specific T cell activity)
- Where available, magnitude of endoscopic improvement, as assessed by change in endoscopic scores (Simple Endoscopic Score Crohn's Disease [SES-CD] for CD or Endoscopic Sub Score within the Mayo Score for UC) relative to baseline, reporting the average decline and 95% confidence intervals [3, 4].

Exploratory Endpoints

Blood, urine, saliva, and stool will be collected for evaluation of biomarkers

Accrual Period: Estimated accrual of 3-4 patients per year for 18-24 months

Study Duration: Approximately 48 months, including follow up

TABLE OF CONTENTS

1	BACKGROUND AND RATIONALE	8
1.1	Inflammatory Bowel Disease:	8
1.3	Description of the Study Agent/Intervention.....	9
1.4	Scientific Rationale and Clinical Justification	11
1.4.1	Rationale for the study of BMSCs in Pediatric IBD	11
1.4.2	PLAN OF STUDY:	13
1.4.3	Rationale for the Dosage and Treatment Period	14
2	STUDY OBJECTIVES AND DESIGN.....	15
2.1	Study Objectives:.....	15
2.1.1	Primary Objective:	15
2.1.2	Secondary objectives:	15
2.2	Study Design	15
2.2.1	Primary Endpoint	17
2.2.2	Secondary Endpoints	17
2.2.3	Exploratory Endpoint	17
2.3	Study Population.....	17
2.4	Recruitment Plan	18
2.5	Informed Consent.....	18
2.6	Eligibility criteria	19
2.6.1	Subject Inclusion Criteria	19
2.6.2	Subject Exclusion Criteria	19
3	Study Agent.....	20
3.1	Preparation Administration, and Dosage.....	20
3.2	Assessment of Subject Compliance	21
3.3	Concomitant Medications and Procedures.....	22
3.4	Prohibited Medications and Procedures	22
3.5	Study Schedule.....	22
3.6	Table 1: Protocol of Events.....	22
3.7	Baseline assessment/screening.....	25
3.8	Treatment Phase (Day 0, 7, 14, 21)	25

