2.2 Study Design

This study is a pilot phase 1 treatment protocol for subjects with moderate to severe CD or UC who have failed to respond to or are intolerant of a biologic. Patients must have had a flexible sigmoidoscopy, colonoscopy or MR enterography within 2 months of enrollment, demonstrating active inflammatory disease.

Two types of patients will be enrolled:

- Moderate to severely active CD subjects (defined in Section 2.4)
- Moderate to severely active UC subjects (defined in Section 2.4)

At the beginning of the trial, a history and physical examination will be obtained, and documentation of baseline co-variates[52]:

CD:

- age
- gender

BMSCs

- ethnicity
- history of abdominal surgery
- duration of time with diagnosis
- age at diagnosis
- disease location
- history of failed biologic use
- history of stricturing/penetrating disease
- positive family history of IBD
- history of perianal disease
- severity and phenotype (Montreal classification for adults, or Paris classification for children)

UC:

- age
- gender
- ethnicity
- age at diagnosis
- history of failed biologic use
- duration of time since diagnosis
- positive family history of IBD)

During the course of the patient's treatment with MSCs, standard of care will be administered by the treating physician, at his/her discretion. There are no specific or "antidotal" therapies. Thus, any toxicity that arises during a patient's participation in this treatment will be managed with supportive measures at the discretion of the treating physician.

Three young adult patients (ages 17≤22 years) will be enrolled, staggered by at least 7 days between patients, and each monitored for toxicity over a period of 73 days. A fixed dose will be studied: 1×10^6 cells/kg administered intravenously (IV) weekly for 4 consecutive weeks. Infusions are administered over the first 28 days, followed by a 45 day monitoring period. The primary outcome is regimen-related toxicity, defined in section 5. Toxicity will be scored as a binary variable indicating occurrence or non-occurrence over a monitoring interval from the start of MSC therapy to 45 days after the last infusion. Based on the planned administration schedule, the total toxicity monitoring period will have duration $28 + 45 = 73$ days.

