If we observe no severe (grade 3 or worse) adverse events in the young adult cohort, we will wait a minimum of 45 days before beginning to enroll 3 more patients, ages 12≤16 years (pediatric cohort). If we observe a severe (grade 3 or worse) adverse event occurring at any time from the start of therapy to 45 days following the last MSC administration in the young adult cohort we will stop the study. If we observe no severe adverse events attributable to MSC administration in the young adult cohort but a

severe (grade 3 or worse) adverse event occurring at any time from the start of therapy to 45 days following the last MSC administration in the pediatric cohort we will stop the study. A maximum of 6 patients will be enrolled. Assuming an accrual rate of 3-4 patients per year, it is anticipated that it will require at least 18 – 24 months to accrue all 6 patients. With the additional 24 months of follow up to evaluate efficacy endpoints noted in Section 2, the anticipated trial duration will be about 48 months.

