3.8 Treatment Phase (Day 0, 7, 14, 21)

On Days 0, 7, 14, and 21, subjects will arrive at the hospital for infusion of study drug, eligibility criteria, laboratory assessments, assessment of AEs/SAEs, collection of serum, saliva, urine and stool, and assessment of clinical indices.

Safety Monitoring Phase (Day 28, 45, 56, 73) +/- 3 days

During this visit, the patient will return to Children's National, or be seen by a local physician for a follow-up visit, physical exam, laboratory assessments, AEs/SAEs assessment, assessment of clinical indices, bloodwork, saliva, urine and stool collected for fecal calprotectin. Assessment of symptoms and screening for adverse events may be done by telephone if necessary.

Follow-up Phase (Day 180, 360, 720) +/- 28 days

Subjects will return to Children's National, or be seen by a local physician, for a physical examination and assessment of clinical indices. If physical examination is obtained by a local physician, reports will be emailed or faxed to the study investigator. Assessment of symptoms and screening for adverse events may be done by telephone if necessary.

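### Forty-five days after the last planned infusion is Day 66, not the stated 73 days, so the minimum wait for the pediatric cohort can end before young-adult monitoring does

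*Protocol*

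**What the plan says.** **Monitoring period.** The Synopsis (Study Design), Section 1.4.2 and Section 2.2 score toxicity as yes or no from the first infusion until 45 days past the last one. Each then converts this to a duration; the Synopsis puts it that "the total toxicity monitoring period will have duration $28 + 45 = 73$ days". Section 2.2 explains the sum: "Infusions are administered over the first 28 days, followed by a 45 day monitoring period". It also says that the young adults are "each monitored for toxicity over a period of 73 days", and the Synopsis has them "staggered by at least 7 days, and monitored for toxicity over a period of 73 days".

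**Dosing and visits.** Section 3.8 states: "On Days 0, 7, 14, and 21, subjects will arrive at the hospital for infusion of study drug". Table 1 (Section 3.6) agrees, with dose 4 on Day 21 and a window of ±3 days. Safety visits follow on Days 28, 45, 56 and 73, each ±3 days. No infusion is listed on Day 28. Up to four more weekly doses are optional, and the safety period then runs 45 days from the last dose given.

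**Stopping rule.** The Synopsis and Sections 1.4.2, 2.2 and 7.1.4 stop the study for a severe (grade 3 or worse) event up to 45 days past the last infusion.

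**Pediatric wait.** If the young-adult cohort has no severe event, the Synopsis says "we will wait a minimum of 45 days after the last MSC administration before beginning to enroll 3 more patients". Sections 1.4.2 and 2.2 omit the starting point; Section 2.2 has "we will wait a minimum of 45 days before beginning to enroll 3 more patients". Section 7.1.4 mentions no wait.

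**The concern.** The 73 days are presented as the length of an interval that ends 45 days after the last infusion. The sum that produces 73 counts from Day 28, which is the end of a four-week block and not an infusion day. The monitoring length and the definition it is meant to express therefore end on different days.

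This matters because the young-adult cohort is there to be observed before children are treated, and a single severe event stops the study. Two things depend on the end date: whether a late event triggers the stop, and when pediatric enrollment may begin. With three patients per cohort, one event in the disputed week decides both.

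**Working it through.** All days count from a patient's first infusion (Day 0).

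**Inputs**
- Last planned infusion: Day 21, window ±3 days (Table 1; Section 3.8)
- Interval after the last infusion: 45 days (Synopsis; Sections 1.4.2, 2.2, 7.1.4)
- Stated monitoring period: 73 days (Synopsis; Sections 1.4.2, 2.2)
- Last two safety visits: Day 56 and Day 73, each ±3 days (Table 1; Section 3.8)
- Minimum stagger between young adults: 7 days (Synopsis; Sections 1.4.2, 2.2)

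**1. The plan's own figure.** 28 + 45 = 73. The sum is correct, but its starting day is Day 28.

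**2. The plan's own definition.** Last infusion + 45 = 21 + 45 = **Day 66**. Shortfall: 73 − 66 = **7 days**.

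**3. Can the dosing window close the gap?** Dose 4 on Day 18 gives 18 + 45 = 63. Dose 4 on Day 24 gives 24 + 45 = 69. The range is Day 63 to 69 and never reaches 73.

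**4. Stopping window against monitoring period.** With dose 4 on Day 21, the stopping window closes on Day 66 and the stated monitoring period on Day 73. Days 67 to 73 are monitored but lie outside the stopping window.

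**5. Pediatric wait against the last safety visit.** Counted as in the Synopsis, the minimum wait ends on Day 66 of the last-treated young adult. The previous scheduled visit was on Day 56, 66 − 56 = 10 days earlier, and the next is on Day 73. A laboratory abnormality arising on Days 57 to 66 is inside even the shorter window, but might be found only at the Day 73 visit. The visit windows do not change the order: the earliest permitted last visit is 73 − 3 = Day 70, and the latest end of the wait in step 3 is Day 69.

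**6. Optional doses.** Assuming weekly dosing continues without a break, dose 8 is on Day 21 + 28 = 49, and 49 + 45 = **Day 94**. For such a patient the 73-day figure does not apply.

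**7. Whose last infusion?** With the minimum stagger, the third patient starts on day 14 of the first patient's calendar and has dose 4 on day 14 + 21 = 35. If the first patient takes eight doses, that patient's last infusion is on day 49, later than the third patient's. The wait would end on day 35 + 45 = 80 or day 49 + 45 = 94 of that calendar, depending on whose last infusion counts. The text does not say.

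**The case against.** **The wait is a minimum and is conditional on a clean cohort.** Read beside the 73-day monitoring, it may be meant to open only once monitoring is complete. It is true that Day 66 is the earliest date and not a required one. But no passage says that the cohort is judged clean only after Day 73. The stopping rule closes 45 days after the last infusion, so on Day 66 the cohort can already be clean under it. The 66/73 conflict and the missing starting point remain.

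**The scoring interval and the stopping window agree as worded.** This stands. A reader might infer that the same late event counts as toxicity under one passage and not under another. The documents do not support that: both intervals end 45 days after the last infusion. The figure that disagrees is the stated duration.

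**Later dates and wider gaps.** A reader might take Sections 1.4.2 and 2.2 to mean 45 days after monitoring ends, 73 + 45 = Day 118, and so claim a spread of 118 − 66 = 52 days. No passage states Day 118; it is one reading of wording without a starting point, and it errs towards later opening. A 13-day gap can also be built by setting Day 63 against Day 76, but that compares the early edge of a dose window with the late edge of a visit window. Neither figure should be used.

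**Other safeguards.** Accrual is 3 to 4 patients a year, screening comes first, and Section 10.1 provides continuous review by the investigator and the Data Review Committee. Section 1.4.2 also bars pediatric enrollment if a serious adverse event has been observed in young adults, with no time limit. These make exposure of a child during the gap unlikely. They do not exclude it: screening may be as late as Day −1, and an event found after opening comes too late for that condition.

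**Conclusion.** The point holds. On the planned four-dose schedule, the interval the protocol defines ends on Day 66 (Day 63 to 69 with the dosing window), while the duration it states for that interval is 73 days. The difference is 7 days.

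Two consequences follow from the text. A severe event on Days 67 to 73 of a four-dose patient is monitored but lies outside the stopping window as worded. And the Synopsis wait can elapse before the last-treated young adult finishes the stated monitoring and has the Day 73 visit. In Sections 1.4.2 and 2.2 the wait has no starting point and could also be read as beginning later.

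The conclusion rests on Table 1 and Section 3.8 for the infusion days. Day 94 for an eight-dose patient assumes unbroken weekly dosing. The documents do not show that the pediatric cohort must open on Day 66 or that a child would in fact be dosed in the gap; they show only that the wording allows it.

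**What to change.** Reconcile the Synopsis (Study Design), Section 1.4.2, Section 2.2, Table 1 (Section 3.6), Section 3.8 and Section 7.1.4, so that the monitoring period, the stopping-rule window and the pediatric wait agree with each other and with the infusion days, including optional doses. State the event from which the wait runs and, since patients are staggered and may receive different numbers of doses, the patient from whom it is counted. Use the same wording wherever the rule appears. Which timing is right is for the sponsor to decide.

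The cost is amendment wording. Depending on the choice made, pediatric enrollment may open some days later, which is small against the planned 18 to 24 months of accrual.

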2.6.2 Subject Exclusion Criteria

- Patient <12 years of age or >22 years of age
- Pregnant or breastfeeding. Serum pregnancy test must be negative at screening for female subjects of childbearing potential. Urine pregnancy test must remain negative at each of 4 infusion visits.

- Patients with toxic mega-colon or intestinal perforation
- Evidence of autoimmune chronic active hepatitis or sclerosing cholangitis.
- Patients with fever > 39° C or clinically significant active infection within 1 week (i.e. chronic infections including Hepatitis B/C or HIV or acute infections, including urinary tract infection and respiratory tract infection)
- Received an agent not approved by the FDA for marketed use in any indication or any small molecule inhibitors (i.e. naltrexone) within 60 days of enrollment.
- Subjects who are taking greater than 20 mg (or if body weight <40 kg, 0.5 mg/kg) of prednisone daily.
- Clinically significant abnormal biochemical and hematological parameters, including:
 - Neutrophil count < 1000 cells/mm³
 - Hemoglobin < 8 g/dl
 - Platelet count ≤ 130 cells/mm³
 - Creatinine ≥ 1.2 x the upper limit of normal
 - Alanine aminotransferase (ALT) and/or aspartate aminotransferase (AST) ≥ 2x the upper limit of normal
 - Conjugated bilirubin greater than 1.2 mg/dL
- Has active infection with enteric pathogens as evidenced by positive microbiological culture of stool or C.difficile toxin PCR.
- Had bowel surgery other than perianal procedures (fistulotomy, seton placement, abscess drainage) within 3 months of enrollment.
- Has uveitis
- Has known pulmonary disease, excluding mild intermittent asthma

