4 POTENTIAL RISKS AND BENEFITS

4.1 Allogeneic BMSC Infusion

To date, serious complications or side effects from MSC infusions have not been described. In the trial by Forbes, et al., of MSCs in the treatment of adults with luminal CD, there was one SAE reported: a subject diagnosed with sigmoid adenocarcinoma at the day 42 endoscopy. The patient was subsequently found to have had low-grade dysplasia on sigmoid mucosal biopsy specimen from the entry endoscopy and there had been a previous recommendation for colectomy because of mucosal atypia within a known proximal rectal stricture. [54] Reported infusion side effects are mild and include headache, hives, fever, congestion, and dysgesia (altered taste). Transfusion reactions and allergic reactions have not been reported in published Phase 1 and II trials.

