7 STATISTICAL CONSIDERATIONS

7.1 Statistical Analysis Plan

7.1.1. Sample size and follow up. A maximum of 6 patients will be treated in this pilot study. It is anticipated that it will require 18-24 months to accrue 6 patients. With the additional 24 months of follow up to evaluate efficacy endpoints noted in Section 2, the anticipated trial duration will be 48 months.

7.1.4. Safety Monitoring and Stopping Rules. For the purpose of safety monitoring, "toxicity" will be defined as a probable or definite regimen related severe (grade 3 or worse) adverse event occurring at any time from the start of therapy to 45 days following the last MSC administration. If we observe 1 severe (grade 3 or worse) adverse event occurring at any time from the start of therapy to 45 days following the last MSC administration in the young adult cohort we will stop the study. If we observe no attributable severe adverse events in the young adult cohort, but do observe 1 severe (grade 3 or worse) adverse events occurring at any time from the start of therapy to 45 days following the last MSC administration in the pediatric cohort, we will stop the study.

7.1.3. Future Trials. If the trial is not stopped early, then the toxicity and efficacy data will be used to plan a future trial of MSC cell therapy in pediatric patients with either CD or UC, including (i) blinded placebo-controlled phase II trials optimizing dose or administration schedule, or (ii) randomized comparison to standard therapies.

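### Neither exclusion list covers malignancy or intestinal dysplasia/atypia, although section 4.1 links the only SAE in the cited adult MSC Crohn's trial to such pathology

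*Protocol*

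**What the plan says.** The exclusion criteria appear twice, in the Synopsis and in section 2.6.2, with the same content. On the bowel they exclude "Patients with toxic mega-colon or intestinal perforation", active enteric infection, and a patient who "Had bowel surgery other than perianal procedures (fistulotomy, seton placement, abscess drainage) within 3 months of enrollment". The other items cover age, pregnancy, autoimmune liver disease and sclerosing cholangitis, fever and infection, unapproved agents, steroid dose, laboratory limits and uveitis. The last item is "Has known pulmonary disease, excluding mild intermittent asthma". No item concerns cancer, dysplasia or atypia, and none lets the investigator exclude a patient on general grounds.

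Section 4.1 summarises an adult trial of MSCs in luminal Crohn's disease, in which "there was one SAE reported: a subject diagnosed with sigmoid adenocarcinoma at the day 42 endoscopy". It adds, on this patient's earlier pathology: "low-grade dysplasia on sigmoid mucosal biopsy specimen from the entry endoscopy and there had been a previous recommendation for colectomy because of mucosal atypia".

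The stopping rule in section 7.1.4 begins: "If we observe 1 severe (grade 3 or worse) adverse event occurring at any time from the start of therapy to 45 days following". For the young adult cohort, the Synopsis, section 1.4.2 and section 2.2 likewise stop the study for one event of that severity, namely an "adverse event occurring at any time from the start of therapy to 45 days following the last MSC administration in the young adult cohort". None of these young adult sentences asks whether the event is related to the cells.

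**The concern.** The risk section accounts for the one reported SAE by a lesion that was there before the cells were given. The eligibility criteria then do nothing to keep out a patient with that kind of lesion, even when it is already on file. Malignancy in general is missing too, although section 1.2 describes a rare lymphoma in pediatric and young adult Crohn's patients on infliximab with 6MP or azathioprine, and the criteria require previous or current biologic treatment and permit that combination.

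What is at stake is the interpretability of a very small safety study. With at most six patients, one event from disease present at entry could weigh heavily on the safety summary and on the decision to open the pediatric cohort, although it would say little about the product.

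**Working it through.** There is no sample-size or power figure to reproduce. The check sets the sections side by side, followed by a short calculation.

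**1. Is the gap closed elsewhere?**
- The inclusion criteria and section 2.3 require active disease and biologic failure or intolerance. Neither mentions pathology.
- The surgery exclusion concerns operations already performed within 3 months, so a patient who has only been advised to have a colectomy passes it.
- The qualifying examination may be up to 2 months old, may be MR enterography alone (so no tissue), and may have been done at an outside facility (section 3.7). No section requires an existing biopsy report to be read.
- Section 6 allows withdrawal before treatment if the patient ceases to meet the entry criteria, which inherits the gap. Its fitness clause allows withdrawal but is not an entry criterion.

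The gap stays open.

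**2. What could one such event do?**
- *Primary endpoint* (section 2.2.1): the frequency of any AE or SAE. Section 5.1 counts adverse changes after first dosing whether or not they are related. A lesion diagnosed after dosing could be counted.
- *Pediatric gate* (section 1.4.2, stated twice): the pediatric cohort opens only if no SAE has been observed in the young adults, with no attribution condition. An event classed as serious could keep it closed.
- *Stopping rule* (section 7.1.4): the operative sentence has no attribution condition, but the sentence before it defines toxicity as a grade 3 or worse event judged probably or definitely related to the regimen. Under section 5.5, an event with evidence of another cause is classed as not related. On the first reading a grade 3 or worse cancer stops the study; on the second it probably does not.

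**3. Window.** The plan's figure reproduces: 28 + 45 = 73 days. Counted from the fourth infusion on Day 21, the window ends on Day 21 + 45 = 66. With four extra weekly doses, the last on Day 49, it ends on Day 49 + 45 = 94.

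**4. How sensitive is a one-event rule?** On the unattributed reading, with the same risk p for each of n patients, the chance of at least one event is 1 − (1 − p)^n. The protocol gives no rate, so every p is an assumption.

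| Assumed p | n = 3 | n = 6 |
|---|---|---|
| 1% | 3.0% | 5.9% |
| 2% | 5.9% | 11.4% |
| 5% | 14.3% | 26.5% |

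Suppose one of the six has a pre-existing lesion, with an assumed 25% chance of a grade 3 or worse event in the window, and the other five have 2% each. The chance is then 1 − 0.98^5 × 0.75 = 32.2%, against 11.4% without that patient. At an assumed 50% it is 1 − 0.98^5 × 0.50 = 54.8%. These figures are conditional on such a patient being enrolled. They do not estimate how often that happens, and they do not apply if only related events count.

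**The case against.** The strongest reply is that the protocol contains no internal error here: nothing promises such an exclusion, and the consequences are easy to overstate. Several parts of that reply stand.

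- A reader might infer that one such cancer would stop the trial. The text does not settle this, because section 7.1.4 also carries the relatedness definition. That conflict is a separate defect of the stopping rule and is not created by the exclusion list.
- A reader might infer that, because the cited cancer appeared at day 42 and every version of the window extends beyond that day, the same would be seen here. But the cited cancer was found at an endoscopy. In this protocol, Table 1 marks endoscopy or MR enterography at screening only, and section 3.9 says any procedure is done for clinical purposes. Table 1's footnote lists SES-CD and Mayo among the activity measures, but the endpoints use endoscopic scores only where available. A silent lesion would surface only through symptoms or a clinically indicated procedure.
- A diagnosis is not automatically an SAE. Section 5.2 requires a listed outcome, or a judgement that the event is medically important.
- The dysplasia in the cited patient was recognised only afterwards. What was on record was atypia with a colectomy recommendation, and section 4.1 does not say that cancer was known at entry.
- A reader might infer that the cells themselves raise cancer risk in such patients. Section 4.1 points to the earlier pathology, and the protocol offers no support for that inference.
- Screening includes medical and surgical history and examination, and section 9 has patients registered after a call to the principal investigator. Known cancer or an outstanding colectomy recommendation would often come up.

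None of this supplies a written criterion. An investigator who learned of the atypia would still find the patient eligible on paper.

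**Conclusion.** The omission is established from the text: both lists lack any malignancy or dysplasia/atypia item, and the protocol's own risk section shows why one is relevant. The consequence is possible rather than certain. Such an event could be counted in the primary endpoint and could hold the pediatric cohort closed. Whether a grade 3 or worse event would stop the study depends on how the conflict in section 7.1.4 is resolved, and those statements must be reconciled separately.

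The probability is low, on the grounds of age and the absence of scheduled follow-up endoscopy, but it cannot be quantified because the documents give no rate. The percentages above show only how little slack a one-event rule leaves in groups of 3 and 6. This is a cheap improvement of low severity.

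**What to change.** Add one line to the exclusion criteria in both the Synopsis and section 2.6.2: known or suspected malignancy, or dysplasia or atypia on any previous intestinal biopsy. Atypia should be named, because an exclusion limited to known dysplasia could have missed the cited patient.

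Add one item to the eligibility checklist mentioned in section 9: before Day 0, review any pathology report already available, including one from the qualifying endoscopy. Table 1 already places an eligibility check on Day 0, so the review has a natural place.

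No new biopsy, endoscopy or visit is needed. The cost is one line in two lists, one checklist item, and a very small loss of eligible patients in this age range.
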